# 3.1.3 Definition of Baseline

Baseline for all efficacy and safety variables will be defined as the last scheduled value obtained prior to the first dose of study drug. If the measurement at this visit is missing, the last measurement prior to the first dose of study drug will be used as baseline. The scheduled baseline visit for all efficacy and safety variables is Day 1 pre-dose.

#### 3.1.4 Summary Statistics

Categorical data will generally be summarized with counts and percentages of patients. The denominator used for the percentage calculation will be clearly defined. Continuous data will generally be summarized with descriptive statistics including n (number of non-missing values), mean, median, standard deviation, minimum, and maximum.

# 3.2 Analysis Populations

# 3.2.1 Intent-to-Treat (ITT) Population

The ITT Population will include all patients who are randomized to the study and will be used to assess efficacy.

## 3.2.2 Per-Protocol (PP) Population

The PP Population will include all patients who are randomized to the study and do not have any major protocol deviations.

A list of patients with major protocol deviations leading to exclusion from the PP Population will be finalized prior to unblinding the randomized treatment assignments.

#### 3.2.3 Safety Analysis Population

The Safety Analysis Population will include all patients who receive any amount of study drug.

## 3.2.4 Pharmacokinetic Population

The Pharmacokinetic Population will include all patients who receive any amount of investigational product and have at least one measurable CIVI 007 concentration.

# 3.3 Subject Data and Study Conduct

#### 3.3.1 Subject Disposition

Counts and percentages of patients who were screened (signed informed consent), discontinued early during screening (screen failures), and randomized will be summarized in total based on all screened patients. Reasons for early discontinuation will also be summarized.

Counts and percentages of patients who were randomized, discontinued early from the study, and completed the study will be summarized by treatment and in total based on all randomized patients. Reasons for early discontinuation will also be summarized.

#### 3.3.2 Protocol Deviations

Protocol deviations will be defined in the Protocol Deviation Plan. Counts and percentages of patients with CSR reportable protocol deviations by deviation category will be summarized by treatment and in total based on all randomized patients.

#### 3.3.3 Analysis Populations

Counts and percentages of patients in each analysis population will be summarized by treatment and in total based on all randomized patients.

#### 3.3.4 Demographic and Baseline Characteristics

The following demographic and baseline characteristics will be summarized:

- Age (years) and age categories (<65 years, ≥65 years)

- Sex
- Childbearing potential
- Race
- Ethnicity
- Baseline Height (cm)
- Baseline Weight (kg)
- Baseline Body mass index (BMI) (kg/m²) and Baseline BMI categories (<30 kg/m², ≥30 kg/m²)

- Baseline PCSK9 (mg)
- Baseline fasting LDL-C (mg/dL)
- Background statin therapy

Demographic and baseline characteristics will be summarized with descriptive statistics or counts and percentages of patients as appropriate by treatment and in total for all randomized patients and each defined analysis population if the analysis population composition is different than all randomized patients.

## 3.3.5 Medical History

Medical history will be coded to system organ class and preferred term using the Medical Dictionary for Regulatory Activities (MedDRA) terminology version 22.0 (or the most recent version available). Counts and percentages of patients with medical history by system organ class and preferred term will be summarized by treatment and in total based on all randomized patients.

# 3.3.6 Concomitant Medications

Concomitant medications will be coded to anatomical therapeutic chemical (ATC) class and preferred term using the World Health Organization (WHO) Drug Dictionary version 2019G B3 (or the most recent version available). For summary purposes, medications will be considered prior medications if they stopped prior to the first dose of study drug and concomitant medications if they were taken at any time after the first dose of study drug (i.e. started prior to the first dose of study drug and were ongoing or started after the first dose of study drug).

Counts and percentages of patients taking concomitant medications by ATC class and preferred term will be summarized by treatment and in total based on the Safety Analysis Population. The use of any prior medication or concomitant medication will be listed for all randomized subjects.

#### 3.3.7 Study Exposure and Compliance

Days of exposure to study will be calculated as date of last visit – date of first dose of study drug + 1. Days of exposure to study will be summarized by treatment based on the Safety Analysis Population with descriptive statistics and with counts and percentages of patients with exposure in the following categories:

- <= 14 days

- 15 28 days
- 29 56 days
- 57 84 days
- >= 85 days

The total number of injections administered will be calculated for each patient. A contingency table will be provided to display the number and percentage of patients in each treatment group with the number of injections.

# 3.4 Efficacy and Pharmacodynamics Assessments

PCSK9 will be collected at Day 1, Day 8, Day 15, Day 22, Day 29, Day 36, Day 43, Day 57 and Day 85 or early termination. Fasting lipid panel (including LDL-C, non-HDL-C, total cholesterol, triglycerides, HDL-C, and VLDL-C) will be collected at each study visit. Fasting apolipoproteins (including apolipoproteins B and A-I, and lipoprotein (a)) and β-Q LDL-C will be collected at Day 1, Day 8, Day 15, Day 29, Day 36, Day 43, Day 57 and Day 85 or early termination.

All the secondary and exploratory efficacy endpoints will be summarized descriptively and analyzed by planned treatment based on ITT Population. All the individual data will be listed.

# 3.4.1 Secondary Efficacy Endpoints Analyses

The PCSK9 and LDL-C will be listed and summarized using descriptive statistics by treatment group over the study period to describe absolute and percent changes from baseline.

The secondary endpoints of the study will be analyzed using analysis of covariance (ANCOVA) models to compare the mean percent change from baseline in LDL-C and PCSK9 approximately 28 days after the first injection (Day 29) and approximately 28 and 56 days after the second injection of study drug (Day 57 and Day 85) between treatment groups with placebo. This ANCOVA model will include treatment as a factor and baseline level as a covariate. The missing values will be imputed by last observation carried forward (LOCF) method.

Normality will be tested for the model residuals and the p-value from the Shapiro-Wilk test will be provided. If the residuals of this model are not normal, then non-parametric analyses (Wilcoxon rank- sum test) will be explored to compare the difference in median percent change between treatment groups.

The presentation of results will be the observed data and include the estimated means by treatment group, their standard errors, and the estimated differences in means between the patient treatments and corresponding 95% confidence intervals and p-values.

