3.2 Study Design Rationale

Based on initial data from the ongoing FIH study and within the context of a limited experience, CIVI 007 appears to provide the expected pharmacologic profile associated with PCSK9 inhibition. CIVI 007 shows PCSK9 knockdown that begins around 12.5 mg with maximal inhibition of approximately 90% at common mg. The efficacy profile includes robust, dose-dependent reductions in atherogenic lipoproteins and lipids that appear to peak within a week following administration and are stable out to 4 weeks after administration. Changes in lipoproteins and lipids after multiple doses are consistent with those after single doses.

CIVI 007 therefore appears to have a favorable clinical profile and justify advancement to Phase 2 testing in this study. The Phase 2a study will provide robust information to determine advancement of the program to Phase 2b/3 testing. A forced up-titration dosing group (cc) mg) will provide an initial understanding of this dosing strategy on CIVI 007's clinical profile.

A parallel group design, as opposed to an ascending dose design, has been chosen as initial Phase 1 observations have demonstrated safety in the study dose range. Subcutaneous dosing has been chosen as this is the intended clinical route of administration.

Dosing and follow-up will occur in a double-blind state for the Investigator and clinical staff in order to avoid bias in the collection of data.

Conducting the study in patients with LDL-C levels in the study range and on a background of a stable dose of statin therapy (with or without ezetimibe) will enable safety, tolerability, PK, and PD data to be collected in the intended clinical population in whom additional drug treatment may be warranted to optimize their LDL-C levels.

Placebo has been chosen as the control treatment to assess whether any observed effects are treatment-related or simply reflect the study conditions.

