5.5.3 Study Drug Administration

CIVI 007 and placebo are sterile solutions to be administered by SC injection.

Dosing is to be in the morning following an overnight fast:

- CIVI 007 (color colomg) is to be administered SC into the abdomen (or thigh or upper arm, if necessary) from a solution at 150 mg/mL (colomg per colomL vial).
- Placebo is to be administered SC into the abdomen (or in thigh or upper arm, if necessary).
 The volume of injection will be randomly assigned to match one of the two active CIVI 007 doses.

Note: For the second dose of CIVI 007 or placebo administration, the investigators should try to avoid using the same injection site area as the first dose. For other permitted concomitant

medications administered subcutaneously, do not administer in same injection site area as the study drug, for at least 2 weeks after the last dose of study drug.

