# 2.2 Study Design

#### 2.2.1 Overview

This is a Phase 2a, randomized, double-blind (investigator/subject), sponsor-open, parallel-group, multicenter study to evaluate the early clinical profile (safety, tolerability, pharmacodynamics and pharmacokinetics) of CIVI 007 in patients on a background of statin therapy with or without ezetimibe. Patients are required to be on standard of care treatment for high blood cholesterol consistent with 2018 ACC/AHA guidelines that includes a stable dose of statin therapy (with or without ezetimibe) for at least 4 weeks prior to the Screening Visit. The study will enroll approximately 48 patients who will be randomized to 1 of 3 active treatment groups or the placebo reference group (12 patients per active treatment group and 12 in the placebo treatment group) across approximately 7 sites in the United States.

All potentially eligible patients will partake in the Screening Visit up to 21 days prior to Day 1. The Screening Visit will be their first study visit. Laboratory values can be retested once during screening for LDL-C that is in the range of 65-69 mg/dL, or for triglycerides in the range of 401-450 mg/dL.

[figure not shown]
The Treatment Period will be approximately 28 days from Day 1 to Day 29; each treatment group will receive 2 administrations of study drug. Eligible patients will be randomized on Day 1 in a 1:1:1:1 ratio to one of the following treatment groups:

- Group 1: mg CIVI 007 administered SC on Days 1 and 29
- Group 2: mg CIVI 007 administered SC on Day 1 followed by mg CIVI 007 administered SC on Day 29
- Group 3: mg CIVI 007 administered SC on Days 1 and 29
- Group 4: Placebo for CIVI 007 administered SC on Days 1 and 29

The Follow-up Period will be approximately 8 weeks and begin following the last dose of study drug, unless extended follow-up is required based on the Day 85 LDL-C assessment or other Investigator determined safety considerations.

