#### 2.2.4 Sample Size Determination

Approximately 48 patients (12 patients per active treatment group, 12 patients per placebo treatment) will be randomized into 1 of 4 treatment groups.

The sample size chosen for this study was not based on power calculations. However, the number of patients in each part of the present study is common in early clinical studies and is considered sufficient to achieve the objectives of the study without exposing undue numbers of patients to study drug.

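### If, as the visible text implies, the up-titration arm starts on the fixed lower dose, a pooled Day 29 contrast would estimate lower dose versus placebo with a 13.4% smaller standard error

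*SAP*

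**What the plan says.** Patients are allocated equally to four groups: "Eligible patients will be randomized on Day 1 in a 1:1:1:1 ratio" (SAP 2.2.1), with "12 patients per active treatment group, 12 patients per placebo treatment" (SAP 2.2.4). Groups 1 and 3 each receive a fixed regimen on Days 1 and 29, and Group 4 receives placebo. Group 2 receives "mg CIVI 007 administered SC on Day 1 followed by mg CIVI 007 administered SC on Day 29" (SAP 2.2.1; milligram values redacted).

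Two protocol passages bear on Group 2's first dose. Section 3.2 calls it "A forced up-titration dosing group". Section 5.5.3 says of placebo: "The volume of injection will be randomly assigned to match one of the two active CIVI 007 doses".

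SAP 3.4.1 names three times for the secondary analysis of percent change in LDL-C and PCSK9. The first is "approximately 28 days after the first injection (Day 29"; the others are Days 57 and 85. One model serves all three: "This ANCOVA model will include treatment as a factor and baseline level as a covariate". The sample code has a four-level treatment factor and three ESTIMATE statements, each setting one active arm against placebo. No contrast combines arms at Day 29. Tests of each active dose against placebo follow a fixed sequence, whose order is not given. If residuals are not normal, a Wilcoxon rank-sum test is to be explored.

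**The concern.** At Day 29, before the second injection, every patient has had one injection. If Group 2 starts on the same dose as the fixed lower-dose arm, the two arms differ in label only up to that point. The plan still treats them as two treatments.

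Two things follow. The lower-dose effect at Day 29 is estimated twice, from 12 patients each time, when 24 are available. And two of the three Day 29 tests ask the same question, so by chance one may reach significance and the other not. Under a fixed sequence, a chance failure in one of these arms could block the test of the other, although both have had the same dose.

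The protocol's rationale (section 1.8) says the data will help set doses and regimen for later phases, so the precision of a dose-specific estimate has practical value.

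**Working it through.** **1. The premise**

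| Source | What it gives |
|---|---|
| Protocol 5.5.3 | Placebo volume is matched to one of two active doses, so two dose levels |
| Protocol 3.1 and 5.1 | Groups 1 and 3 are fixed; Group 2 has one dose on Day 1, then another on Day 29 |
| Protocol 3.2 | Group 2's titration is upward |

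With two dose levels and an upward step, Group 2's first dose is the lower level, which is also the fixed lower-dose arm's first dose. This is an inference, because the milligram values are redacted.

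**2. The plan's own figure**

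The SAP gives no power, SD or effect size: "The sample size chosen for this study was not based on power calculations". The only figure to reproduce is the total, 4 × 12 = 48, which agrees.

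**3. Precision of lower dose versus placebo**

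In SD units, ignoring small baseline imbalance, the variance is 1/n(active) + 1/n(placebo).

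- One arm: 1/12 + 1/12 = 0.1667; SE = 0.408.
- Two arms pooled: 1/24 + 1/12 = 0.1250; SE = 0.354.
- Variance ratio: 0.1250/0.1667 = 0.75, so a single-arm contrast keeps 75% of the attainable information and loses 25%.
- SE ratio: √0.75 = 0.866, a reduction of 13.4%.

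**4. 95% confidence interval half-width**

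With complete data the residual degrees of freedom are 48 − 5 = 43, and t = 2.017. The half-width is t × SE × SD. No SD is given, so a range is assumed.

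| Assumed SD (points) | Separate, 12 v 12 | Pooled, 24 v 12 |
|---|---|---|
| 10 | 8.2 | 7.1 |
| 20 | 16.5 | 14.3 |
| 30 | 24.7 | 21.4 |

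**5. Power and contradictory results**

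These figures assume two-sided 0.05 (inferred from the 95% intervals) and a true effect equal in both arms. Power is from the noncentral t distribution. The last column is from simulation of two 12-patient arms sharing one 12-patient placebo group, with 43 degrees of freedom.

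| Assumed effect (SD) | Power, one arm | Power, pooled | The two separate tests disagree |
|---|---|---|---|
| 0.75 | 44% | 55% | 32% |
| 1.0 | 67% | 79% | 29% |
| 1.25 | 85% | 93% | 18% |
| 1.5 | 95% | 99% | 8% |

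**6. Is any information discarded?**

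The simple average of the two separate contrasts has variance 1/12 + (1/4)(1/12 + 1/12) = 0.1250, the same as pooling. The model therefore already holds the information. What is missing is a planned contrast that reports it with its own interval.

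**The case against.** Nothing planned is invalid. Comparing each randomized arm with placebo is standard and unbiased, and it is needed at Days 57 and 85, when the regimens differ. Keeping one arm structure at all visits is a legitimate choice, and chance differences between two arms on the same dose are ordinary sampling variation. All of this stands.

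The gain may also be small in practice. The trial is Phase 2a with safety as its primary objective. The protocol reports maximal PCSK9 inhibition of about 90% and robust lipid reductions. At effects of 1.5 SD or more, a single arm already has about 95% power. That limits the importance of the point, though no SD is given to show which case applies, and the narrower interval is useful for dose selection at any effect size.

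Three stronger readings are tempting and are not supported:

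- **That half the lower-dose information is wasted.** Half describes only the number of patients behind each lower-dose mean (12 of 24). For the planned comparison the placebo group stays at 12 and the loss is 25%. Both arms also contribute to the common residual variance.
- **That the documents state equal first doses.** They do not. The count of two doses rests on one sentence about placebo volume. The parallel sentences in the protocol synopsis and SAP 2.2.3 give no count.
- **That the secondary analysis loses precision at every earlier visit.** The secondary ANCOVA covers only Days 29, 57 and 85. Percent changes in LDL-C and PCSK9 at other visits are summarized descriptively, apart from the optional repeated-measures model.

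A pooled contrast also needs more than a line of code: a multiplicity status, a pre-dose restriction and a Wilcoxon counterpart. These belong in the fix and do not count against it.

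**Conclusion.** The point holds as an efficiency improvement, conditional on equal first doses. At Day 29 the plan gives up 25% of the attainable information on lower dose versus placebo. Pooling lowers the standard error from 0.408 to 0.354 SD and replaces two answers to one question with a single estimate.

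This rests on the first-dose inference, 12 evaluable patients per arm, a common residual variance, and Day 29 samples drawn before the second injection. The half-widths also depend on the assumed SDs, and the power and disagreement figures on the assumed effects. The separate-arm results remain valid whether or not the contrast is added.

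**What to change.** Check the unredacted doses first. If Group 2's first dose differs from the fixed lower dose, make no change. If they are equal, amend SAP 3.4.1 as follows:

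1. Add a pre-specified pooled contrast to the Day 29 ANCOVA, in the SAP's coding order (placebo, 1, 2, 3): `TREATMENT -1 0.5 0.5 0`, or `TREATMENT -1 0 0.5 0.5` if arm 3 is the lower dose. Report it as the Day 29 lower-dose estimate.
2. State its multiplicity status. Either label it supportive and outside the fixed sequence, or give it a place in the sequence instead of the two duplicate lower-dose tests.
3. Restrict it to samples taken before the second injection. Protocol 6.2.4 lists the Day 29 lipid and PCSK9 draws ahead of dosing but does not label them pre-dose. The Day 29 window in SAP 3.1.2 for unscheduled and early-termination visits runs to Day 32, so post-dose values assigned to Day 29 must be excluded.
4. If the Wilcoxon test is used at Day 29, combine the two arms for that test.
5. Keep the randomized arms separate after the second injection, including at Days 57 and 85.

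The cost is one extra ESTIMATE statement and a few sentences of text. Trial conduct and data collection do not change. The downside is one more contrast, whose multiplicity status has to be stated.

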1.2 Summary of Preclinical Pharmacology

1.2.1 Primary Pharmacodynamics

In monkeys administered CIVI 007 at 0.5 and 1.5 mg/kg once weekly for 4 weeks via the subcutaneous (SC) route, the PCSK9 protein in serum was reduced by compared to the baseline level, respectively. The maximum effect was achieved on Day 29, and PCSK9 levels did not fully return to pre-study values during the 8-week recovery phase. The effects were substantially greater than those seen with (the oligonucleotide moiety of CIVI 007, without GalNAc conjugate), underpinning the ability of the GalNAc moiety to drive effective liver delivery.

In the same study, CIVI 007 caused dose responsive LDL-C reductions of 53% and 70% compared to baseline, respectively, with maximum effect on Day 29; the half-life for reversal of the LDL-C reductions was days, respectively. As expected, LDL reductions were tracked by apolipoprotein (apo) B reductions. On Day 29, apoB levels were down dose dependently by respectively, and apoB levels did not return fully to baseline during the 7 weeks of recovery in either of the 2 dose groups. Weak or no effects on high-density lipoprotein cholesterol (HDL-C), total cholesterol, and triglycerides were observed.

The administration route seemed to have an effect on the intended pharmacology (serum PCSK9, plasma apoB, and LDL-C), with the intravenous (IV) route being significantly less effective than the SC route. Receptor saturation differences might account for an apparent greater effect with the more protracted distribution phase associated with SC administration than with the shorter distribution phase associated with IV administration.

[figure not shown]

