The Follow-up Period then begins and patients will attend scheduled follow-up visits at Days 36, 43, 57 and 85 to assess safety, tolerability, PK, and PD. The duration of the Follow-up Period will therefore be approximately 2 months from the last dose of study drug, unless extended follow-up is required based on Day 85 LDL-C assessments or other Investigator determined safety considerations.

[figure not shown]
Extended follow-up visits will be conducted on a monthly basis for up to 3 months if Day 85 LDL-C levels are <80% of their baseline level; extended follow-up will end within the 3-month period if LDL-C levels are ≥80% of baseline. Extended follow-up visits (frequency and assessments will be at the discretion of the Investigator) to monitor Investigator determined safety considerations may extend beyond 3 months, if deemed appropriate by the Investigator, and will continue until there are no safety observations requiring further follow-up. The total duration of

the study for each patient will be approximately 3 to 6.5 months, depending on the variable length of the screening, and follow up periods.

A Safety Review Committee (SRC) will perform interim unblinded reviews of safety, tolerability, and available PK and PD data collected for the purposes of protecting subject safety as well as providing guidance to the Sponsor on the evolving clinical profile of CIVI 007. The SRC will comprise, at a minimum, the Sponsor's clinical development contact, the study Medical Monitor, a gastroenterologist not involved in study conduct and a pharmacokineticist. A separate document will detail the SRC's operating procedures.

The study design is graphically summarized in Figure 1:

Figure 1. Summary of the Study Design

Mo = month; Q4W = Every 4 weeks; Wk = week; R = randomization;

A visit window of ± 3 days will be permitted for each study visit except for the first day of study drug administration.

Appendices A and B define the detailed Schedule of Procedures and Clinical Laboratory Analyte measures, respectively, to be performed during the study.

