5.2 Rationale for Dosing

Standard antisense molecules have been demonstrated to scale allometrically between the mouse, monkey, and human based on body weight. Accordingly, with a NOAEL in monkeys of 30 mg/kg, the doses of and an average body weight of 60 kg) is > CCI - fold below the NOAEL.

More importantly, based on initial data from the ongoing FIH study and within the context of a limited experience, CIVI 007 appears to provide the expected pharmacologic profile associated with PCSK9 inhibition. CIVI 007 shows PCSK9 knockdown that begins around 12.5 mg with maximal inhibition of approximately 90% at mg. The efficacy profile includes robust, dosedependent reductions in atherogenic lipoproteins and lipids that begin within 1 week of administration and are stable out to 4 weeks after administration. Changes in lipoproteins and lipids after multiple doses are consistent with those after single doses.

There were no obvious drug-related safety findings in the dose range of 12.5 to a mg. Grade 1 ALT elevations appeared in both placebo and active doses with similar frequency. At higher doses, and based on higher levels of ALT increase, a signal of hepatotoxicity was apparent at 300 mg with a potential signal in one subject at 150 mg that was confounded with alcohol intake at the time of liver testing.

CIVI 007 therefore appears to have a favorable clinical profile at lower doses and these justify advancement to Phase 2a testing in this study.

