6.5 Early Termination Visit and Withdrawal Procedures

The end of treatment for patients completing the study is the Day 85 visit. For patients who are withdrawn from the study prior to completion, all Day 85 procedures will be performed at an early termination visit. These procedures include the following:

- Perform full physical examination.
- Record vital signs and weight.
- Collect urine sample for urinalysis assessment.

- Perform urine pregnancy test.
- Collect blood samples for clinical safety chemistry panel, coagulation, and hematology assessments.
- Collect blood samples for fasting lipid panel assessment.
- Collect blood samples for fasting apolipoproteins and LDL-C (beta-quant).
- Collect blood samples for hsCRP, PCSK9, and fibrinogen analysis.
- Collect blood samples for anti-drug antibody analysis
- Collect blood samples for sparse PK, cytokine panel and complement activation analysis.
- Perform 12-lead ECG measurements.
- Record adverse events.
- Record concomitant medications.

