#### 3.1.2 Analysis Visits

Scheduled visits will be assigned to analysis visits as recorded on the case report form (CRF). Unscheduled and early termination visits will be assigned to analysis visits according to the following visit windows:

Analysis Visit	Target Analysis Day	Low Analysis Day	High Analysis Day
Day 8	8	2	11
Day 15	15	12	18
Day 22	22	19	25
Day 29	29	26	32
Day 36	36	33	39
Day 43	43	40	46
Day 57	57	47	71
Day 85	85	72	85 or End of Study (if Last
			Observation > Day 85)

Within an analysis visit window, the measurement from the visit closest to the defined target analysis day will be used. If there is more than one measurement with equal distance to the defined target analysis day, the latter will be used. If no visits occur within a visit window, the measurement for this visit will be treated as missing.

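### LOCF in the main ANCOVA can overstate Day 85 lowering in the fixed-dose arms if the effect wanes; the MMRM without imputation should lead, not be optional

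*SAP*

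**What the plan says.** **Analysis.** SAP 3.4.1 compares percent change in LDL-C and PCSK9 with placebo at Days 29, 57 and 85 by ANCOVA, adjusting for baseline, and adds: "The missing values will be imputed by last observation carried forward (LOCF) method". SAP 3.4.2 applies the same rule to the exploratory endpoints. SAP 3.4.1 also permits, without requiring, an MMRM with no imputation as a robustness check; it does not name that model's response variable. The same section and Protocol 9.2.2 say that the results presented will be observed data. The protocol does not mention LOCF.

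**Who is missing at Day 85.** For withdrawals, Protocol 6.5 says that "all Day 85 procedures will be performed at an early termination visit". SAP 3.1.2 then assigns an unscheduled or early-termination visit on days 47 to 71 to Day 57, and one from day 72 onward to Day 85. It continues: "If no visits occur within a visit window, the measurement for this visit will be treated as missing".

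**Time course.** Protocol 3.2, drawing on limited first-in-human experience, says that lipid reductions "appear to peak within a week following administration and are stable out to 4 weeks after administration"; Protocol 5.2 says that they "begin within 1 week of administration and are stable out to 4 weeks after administration". Neither says what follows. In monkeys (Protocol 1.2.1), "PCSK9 levels did not fully return to pre-study values during the 8-week recovery phase", and apoB had not fully recovered by 7 weeks. The same section reports that "the half-life for reversal of the LDL-C reductions was" a number of days that is redacted. Protocol 3.1 provides for either course: "Extended follow-up visits will be conducted on a monthly basis for up to 3 months if Day 85 LDL-C levels are" below 80% of baseline.

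**The concern.** Carrying a value forward assumes that nothing changes after the patient was last seen. That is reasonable while the effect is on its plateau. It is least secure between Day 57 and Day 85, which runs from 4 to 8 weeks after the last dose.

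Day 85 is the only secondary time point beyond the described plateau, so it is where persistence is estimated. Protocol 1.8 says that the PD data will help to set the doses and regimen for Phase 2b and 3. Descriptive summaries and listings will also show persistence, but the estimate, interval and p-value against placebo come from the LOCF model. With 12 patients per arm, each leaver carries 1/12, about 8%, of the arm mean.

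**Working it through.** The plan gives no figure to reproduce, because the sample size was not based on power.

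**Inputs.** From the documents: 12 patients per arm, two doses (Days 1 and 29), and the visit windows above. Assumed, because the documents give none of them: number of leavers *d*, recovery *R* between the last value and Day 85 (percentage points), SD of percent change, and a flat placebo arm.

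**Who is affected.** Patients in Groups 1 and 3 last seen after dose 2 and with no visit from Day 72 onward. A patient who terminates on day 60 is assigned to Day 57, so Day 85 is filled with a value from about 4 weeks after dose 2.

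**Plausible recovery.** With an assumed 40% lowering at Day 57 and a reversal half-life of *h* days, *R* = 40 × (1 − 2^(−28/h)). This gives 30.0, 20.0 and 11.7 points for *h* = 14, 28 and 56.

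**Bias** = (d/12) × R, in points of overstated lowering:

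| Leavers | R = 0 | R = 10 | R = 20 | R = 30 |
|---|---|---|---|---|
| 1 | 0 | 0.8 | 1.7 | 2.5 |
| 2 | 0 | 1.7 | 3.3 | 5.0 |
| 3 | 0 | 2.5 | 5.0 | 7.5 |

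The protocol synopsis allows non-completers to be replaced. If replaced patients stay in the ITT set, the factor is d/(12+d): 1/13 × 20 = 1.5, 2/14 × 20 = 2.9, 3/15 × 30 = 6.0.

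**Against the SE, LDL-C.** The simple SE of a difference is SD × √(2/12) = 18 × 0.408 = 7.3. The fitted LOCF model gives about 7.5 to 7.9, because the carried values add spread. The biases of 1.7, 3.3 and 7.5 are then 22%, 44% and 95% of the SE; the last is level with the simple SE. Over a wider grid (plateau 40 to 60%, Day 85 lowering 0 to 30%, SD 15 to 30, 1 to 3 missing), the bias is below the simple SE in 81% of settings.

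**Against the SE, PCSK9.** Assume a 90% plateau, 30% lowering at Day 85 and 2 leavers: 2/12 × 60 = 10.0 points. The SE is 6.1, 8.2 and 10.2 for SD 15, 20 and 25, so the ratio is 1.63, 1.22 and 0.98.

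**Simulation** (4 arms of 12, SD 18, within-patient correlation 0.6, random leavers in one fixed-dose arm last seen on Day 57, 3000 runs; MMRM unstructured on Days 29, 57 and 85). Negative bias means that lowering is overstated.

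| Setting | LOCF bias, coverage | MMRM bias, coverage | RMSE, LOCF v MMRM |
|---|---|---|---|
| 1 leaver, R = 20 | −1.7, 95% | 0.0, 96% | 7.56 v 7.46 |
| 2 leavers, R = 20 | −3.3, 94% | 0.0, 96% | 8.04 v 7.50 |
| 3 leavers, R = 30 | −7.5, 86% | 0.0, 95% | 10.64 v 7.93 |
| 3 leavers, R = 0 | −0.4 | −0.4 | 7.55 v 7.85 |

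**Leaving related to response.** ANCOVA on observed values is not a safe substitute. With R = 20, if the 3 weakest Day 57 responders leave, the bias is −2.9 (LOCF), −4.2 (observed ANCOVA) and 0.0 (MMRM). If the 2 strongest leave, it is −4.7, +3.3 and +0.3.

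**Choice of visits.** If the 2 weakest Day 43 responders leave after Day 43, a model on Days 29, 57 and 85 alone keeps a bias of about −1.2 in one run and −1.6 in another (LOCF −1.7 and −2.0). A model that also uses Days 36 and 43 brings it to about 0. The full eight-visit unstructured model is not among the simulations reported here.

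**The case against.** **The bias is hypothetical and often small.** This stands. It needs leavers and waning, and the documents establish neither. The monkey data cut both ways: incomplete recovery at 7 to 8 weeks is also evidence of persistence. With 1 or 2 leavers, coverage hardly moves, and without waning LOCF has the slightly lower RMSE.

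**The plan has protections.** This stands in part. Withdrawing patients are asked for the Day 85 panel, a visit from Day 72 counts as Day 85, and patients who change statin or ezetimibe dose stay in the study. None of this helps a patient whose last visit falls before Day 72.

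**Requiring the MMRM as a sensitivity analysis would be enough.** That would expose the problem without departing from the protocol's ANCOVA. However, the lead Day 85 estimate would still rest on the assumption least suited to that visit, when the SAP already names a better model.

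**Stronger readings that the documents do not support.** A reader might infer that Day 85 lowering will be overstated in every active arm. In Group 2 the direction is not fixed, since a leaver before Day 29 carries the effect of the first dose only. For leavers before Day 8, the SAP does not say whether baseline is carried. If it is, lowering is understated: 1/12 × 20 = 1.7 points for 1 leaver where the true lowering is 20. A reader might also see a flat contradiction between LOCF and the observed-data sentence. That sentence could mean observed summaries shown beside model estimates, so it needs clarifying.

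**Conclusion.** The point holds in conditional form. If the effect wanes between 4 and 8 weeks after dose 2, LOCF overstates Day 85 lowering in Groups 1 and 3 in proportion to the patients last seen after dose 2 and before Day 72. Plausible sizes are 1.7 to 3.3 points, with 7.5 at the upper end of the examples; without leavers or waning there is no bias. For LDL-C at SD 18 the examples stay below the fitted SE. That is a property of the assumed inputs and not a general bound: for PCSK9, or with larger recovery and smaller SD, two leavers can exceed it. Days 29 and 57 should be little affected while the plateau holds.

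The study is unpowered, its primary objective is safety, and this endpoint is secondary. The trial's main conclusions are not at risk. The gain is a more accurate estimate of persistence at little cost.

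**What to change.** - Make the MMRM in SAP 3.4.1 the main analysis for Days 29, 57 and 85. State that its response is percent change from baseline, and that it assumes missingness depends only on observed values.
- Document the departure from the ANCOVA named in the protocol synopsis and Protocol 9.2.2.1.
- Pre-specify a covariance fallback. Unstructured on all eight post-baseline visits needs 8×9/2 = 36 parameters; on Days 29, 36, 43, 57 and 85 it needs 5×6/2 = 15. If that fails to converge, use a structure suited to gaps of 7, 14 and 28 days. Use a Day 29/57/85 model (3×4/2 = 6) only as a last resort, noting the bias it leaves when patients leave after Day 36 or 43 because of their response.
- Keep LOCF in 3.4.1 and 3.4.2 as a labelled sensitivity analysis, and say whether baseline is carried forward when there is no later value.
- Keep ANCOVA on observed values as supportive only, stating that it assumes missingness is unrelated to earlier response.
- Reconcile the observed-data sentence in SAP 3.4.1 and Protocol 9.2.2 with whatever is chosen.

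The cost is SAP text, a documented protocol departure, and an interval that can be about 4% wider when there is no waning (simulated SE 7.68 against 7.40 with 3 leavers).
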